# 9.3.4 Co-morbidities (medical history, concomitant diseases)

Co-morbidities are any medical findings, whether or not they pertain to the study indication, that were present before start of therapy with Betaferon, independent on whether or not they are still present. They have to be documented in the Medical History / Concomitant Diseases section. Concomitant diseases of special interest are depression, anxiety, and fatigue.

For any co-morbidity, the diagnosis, the start and the stop date/ongoing have to be documented.

## 9.3.5 **Prior and concomitant medication**

All medication taken before study start (initiated and stopped before study start) is termed prior medication. Prior medication meeting the criteria listed below are considered to be relevant to the study indication have to be documented:

- disease-modifying drugs or immunosuppressants for treatment of MS
- medication to treat MS associated symptoms like depression, fatigue or spasticity

All medication taken in addition to the product for any indication (either initiated before study start or during the study) is termed concomitant medication.

Information to be collected for medication includes: trade name or INN, start date, stop date/ongoing, dose, unit, frequency, application route, indication.

# 9.3.6 Exposure / treatment

Information on Betaferon to be documented include:

- Start and stop date
- Dose
- Expected number of treatment days
- True number of treatment days
- injection-site reactions (yes vs. no; if yes: redness, other discoloration, hematoma, induration, lipodystrophy, necrosis; if yes: mild, moderate, severe)
- flu-like symptoms (yes vs. no)
- Prophylactic analgesic use prior to injection (yes vs. no)

# 9.3.7 Assessment of therapy

N/A

# 9.3.8 Visits

- Initial visit: baseline
- Follow-up visit 1: after approximately 6 months
- Follow-up visit 2: after approximately 12 months
- Follow-up visit 3: after approximately 18 months
- Final visit: after approximately 24 months

## 9.4 Data sources

The investigator collects historic data (demographic and clinical characteristics) from medical records if available. Likewise, the investigator collects treatment related data during visits that take place in routine practice. Each patient is identified by a unique central patient identification code, which is only used for study purposes. For the duration of the study and afterwards, only the patient's investigator is able to identify the patient based on the patient identification code.

# 9.5 Study Size

Based on the following considerations we plan to enroll a total of 250 patients into our study:

We have performed a sample size calculation based on an Analysis of Variance (ANOVA) aiming to identify the number of patients needed to detect a given difference in compliance between three groups of patients, since the maximum number of groups or categories for our covariates under investigation will be three (e.g. smoking [current, past, never]). Most of the covariates have only two categories (e.g. participation in the BETAPLUS® program [yes, no]). There are no data available as to which change in compliance might be regarded as clinically meaningful; however, following internal and external discussions we think that a 7-10% change should be achieved. We have conservatively chosen a 7% difference.

In *table 1* we present the maximum sample sizes needed to detect a difference of 7% in the overall comparison for a predictor with three groups/categories assuming an alpha=0.1in order to have a power of 80%. The sample size is given for a range of standard deviations (SD; 8%, 10%) and assuming different distributions for the predictor groups/categories (1:1:1, 5:2:1).

*Table 1*: sample size calculation for the overall comparison (alpha=0.1)

Difference in compliance (%)	SD 8%		SD 10%		
	Group ratio	Group ratio	Group ratio	Group ratio	

	1:1:1	5:2:1	1:1:1	5:2:1
7	63	128	99	192

As sketched in the table 63 patients would be needed for example to detect a difference of 7% if the standard deviation is 8% and the group ratio 1:1:1. For an extreme group ratio of 5:2:1 the required sample size would be 128. If the standard deviation is 10% we would need a sample size of 192 for a group ratio of 5:2:1.

Hence, in order to be able to detect potential differences with sufficient confidence we would need analyzable data from 192 patients.

The required sample size to detect a difference of seven percent with the same power (80%) will be lower, if a covariate has less than three categories. Further, the sample size will be lower if the true difference in compliance due to a covariate is larger than 7%.

To further account for 20% incomplete or missing data with respect to our primary outcome variable "compliance" (measured in percentage) over the 2 year follow-up we would need to enroll a total of 240 patients. This adjustment is necessary, since for patients who drop out of the study and/or do not wish to have their data read out of the device as well as those lost to follow-up accurate calculation of compliance will not be possible.

Categorical covariates identified as potential predictors in the overall test will be further analyzed using pairwise comparisons, which will affect sample size.

Hence, in *table 2* we present the maximum sample sizes needed to detect a difference of 7% in the pairwise comparison for a predictor with three groups/categories assuming an alpha=0.05 in order to have a power of 80%.

Table 2 : sample size calculation for the pairwise comparison (alpha=0.05)					~ -
Tuble 2. sample size calculation for the pairwise comparison (alpha $=0.05$ )	Table 2. cample size	calculation for the	nairwise com	naricon (alnha–()	(15)
	Tuble 2. sample size	calculation for the	pair wise com	parison (arpha–0	.05)

Difference in compliance (%)	SD 8%		SD 10%		
	Group ratio	Group ratio	Group ratio	Group ratio	
	1:1:1	5:2:1	1:1:1	5:2:1	

7	66	128	99	200
---	----	-----	----	-----

As sketched in the table 66 patients would be needed for example to detect a difference of 7% if the standard deviation is 8% and the group ratio 1:1:1. For an extreme group ratio of 5:2:1 the required sample size would be 128. If the standard deviation is 10% we would need a sample size of 200 for a group ratio of 5:2:1.

Hence, in order to be able to detect potential differences with sufficient confidence we would need analyzable data from 200 patients.

To further account for 20% incomplete or missing data with respect to our primary outcome variable "compliance" (measured in percentage) over the 2 year follow-up we would need to enroll a total of 250 patients.

## Subgroup analysis with respect to the PTMS program

For the secondary objective of evaluating an association between participation in the PTMS program and adherence we will have >90% power to detect a difference of 7% based on a t-test assuming various group sizes (assumptions: 7% difference in compliance between PTMS centers and non-PTMS centers; SD 8% or 10%; alpha=0.05; group sizes: 30 vs. 100, 30 vs. 220, 60 vs. 190, 90 vs. 160).

Sample size calculation was performed using the "proc power" procedure with the "one way anova" statement in SAS 9.2.

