As part of the study we also plan to evaluate whether the **P**sycho-educative **T**raining for patients with **MS** (PTMS) may affect treatment adherence among patients using Betaferon®. The PTMS program is group-based trainings program that has been developed in 2009 and has been advanced since. It aims at helping patients deal with their MS as well as supporting them in developing a positive perspective of their lives, despite suffering from a chronic condition. The key focuses of the program are adequately coping with the disease, self-motivation for the required therapy, and continuity of treatment to ensure compliance/adherence.

The PTMS has been developed by a group of collaborating neurologists and psychologists. We have identified six neurology clinics, specialized in the treatment of MS offering the program as part of their clinical routine.

During clinical routine, the MS nurse or the treating neurologist recommends participation in the PTMS program if there is indication for inadequate coping, incompliance or deficit in knowledge about the disease. In general this pertains to all newly diagnosed patients, but also for example to experienced patients with "needle fatigue". Interested patients with the confirmed diagnosis of MS will be evaluated by a group leader. Exclusion criteria are severe depression or severe cognitive impairment. Groups consist of six to ten patients. The 90 minute sessions will be held with one to two weeks between each session until a series of 10 sessions has been completed. Sessions are mostly led by an experienced psychologist or MS nurse; however, sessions three, four and nine will be led by a physician or social worker. The program comprises knowledge transfer, exchange of experiences, role play, discussions, and self-reflection via diary.

The endpoints pertaining to the evaluation of the PTMS program, coping mechanisms, and social support will only be evaluated in patients from the six centers offering the program.

Approximately 90% of Betaferon® patients in Germany participate in the BETAPLUS® nurse support program. Hence, a subgroup analysis among those patients—while feasible—may not yield additional information and is not planned.

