#### 8.2 Secondary objective(s)

Secondary objectives are to evaluate at each visit:

- Satisfaction with the BETACONNECTTM autoinjector,
- Injection site pain,
- Flu-like symptoms following Betaferon® application,
- Analgesic use prior to Betaferon® application,
- Intake of vitamin D, other vitamins, and nutrients,
- If adherence to Betaferon® treatment is associated with:
  - depression,
  - health related quality of life,
  - coping mechanisms\*,
  - self-management mechanisms,
  - social support\*,

- fatigue, and
- cognition.
- If adherence to Betaferon® treatment at 12 (24) months is associated with number of relapses at 12 (24) months.
- If adherence to Betaferon® treatment at 12 (24) months is associated with EDSS change at 12 (24) months.
- If adherence to Betaferon® treatment is associated with utilities of treatment (only baseline and final visit).
- With respect to the subgroup of patients participating in the PTMS program (participants from PTMS centers vs. participants from non-PTMS centers):
  - At each visit, if the PTMS program is associated with:
    - treatment adherence,
    - depression,
    - quality of life,
    - self-management mechanisms,
    - fatigue,
    - cognition.
- In the subgroup of patients participating in the PTMS program:
  - At each visit evaluation of:
    - social support,
    - coping behavior.

\*only for patients participating in the PTMS program.

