#### 9.7.5 Analysis of secondary outcome(s)

Descriptive statistics will be used to summarize data from questionnaire scales and scores as well as clinical data using mean ( $\pm$  SD), median, minimum, maximum for continuous variables, and category

counts and frequencies (percentages) for categorical variables. Concomitant diseases on the case report form correspond to MedDRA terms. Concomitant medication will be coded using WHO's drug dictionary. Data will be recorded at each of the visits which will enable us to acknowledge and evaluate changes over time.

We will perform analyses for data obtained at each of the scheduled visits.

We will use linear or logistic regression analysis (depending on the outcome scale) to evaluate the association between participation in the PTMS program and adherence to Betaferon® treatment as well as between participation in the PTMS program and depression, health related quality of life, self-management mechanisms, fatigue, and cognition at each visit as well as change of these variables over time.

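### The PTMS comparison is defined by centre in 8.2 and 9.5 but analysed by individual participation in 9.7.5, and its >90% power leaves out the plan's own 20% missing data and the centre effect

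*Protocol*

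**What the plan says.** Section 8.2 sets the PTMS objective as a comparison of "participants from PTMS centers vs. participants from non-PTMS centers". The PTMS part of section 9.5 claims that "we will have >90% power to detect a difference of 7% based on a t-test assuming various group sizes". Its inputs are a "7% difference in compliance between PTMS centers and non-PTMS centers" and "SD 8% or 10%; alpha=0.05", with group sizes 30 vs 100, 30 vs 220, 60 vs 190 and 90 vs 160.

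Section 9.7.5 plans linear or logistic regression to "evaluate the association between participation in the PTMS program and adherence", and the same for depression, quality of life, self-management, fatigue and cognition.

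Section 7 describes how patients enter the programme, which six clinics offer. The MS nurse or neurologist "recommends participation in the PTMS program if there is indication for inadequate coping, incompliance or deficit in knowledge about the disease". In general this covers all newly diagnosed patients, and also experienced patients with needle fatigue. Interested patients are then assessed by a group leader. "Exclusion criteria are severe depression or severe cognitive impairment".

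Elsewhere in section 9.5 the main sample size is raised for "20% incomplete or missing data with respect to our primary outcome variable", which takes 200 analysable patients to 250 enrolled. The protocol calls this adjustment necessary.

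**The concern.** The centre contrast and the participation contrast answer different questions. All patients at a PTMS centre count as exposed under the first, but only those who joined the programme under the second. Participation depends partly on compliance and coping, and is closed to patients with severe depression or severe cognitive impairment. Compliance, depression and cognition are also outcomes of the comparison. A difference between participants and others could then reflect who was referred, who volunteered and who was barred, rather than the programme.

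The power statement describes the centre contrast but treats patients as independent and assumes complete data. If outcomes are correlated within centres, an analysis without a centre term gives intervals that are too narrow, and the stated power is too high. The practical risk is that a PTMS result, positive or null, is read with more confidence than the design supports.

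**Working it through.** **1. The contrast.**
- 8.2: by centre.
- 9.5: opens with participation, then defines the 7-point difference by centre.
- 9.7.5: by participation. Participation yes/no is recorded at the initial visit (9.2.7), so this regression can be run exactly as worded.
- Section 7 also confines the PTMS endpoints to patients from the six centres. Read literally, that leaves no comparator from other centres.

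**2. Reproducing the stated power.** Inputs from 9.5: difference 7, SD 8 or 10, alpha 0.05 (taken as two-sided; the protocol does not say). SE = SD × √(1/n₁ + 1/n₂), noncentrality δ = 7/SE, df = n₁ + n₂ − 2, exact noncentral t. Example, 30 vs 100 at SD 10: SE = 10 × √(1/30 + 1/100) = 2.082, δ = 3.363, df = 128, power 91.6%. All eight combinations exceed 90%, so the stated figure reproduces.

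**3. Applying the plan's 20% missing data.** Each group is multiplied by 0.8.

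| Group sizes in 9.5 | Analysable | SD 10, as stated | SD 10, 20% missing | SD 8, as stated | SD 8, 20% missing |
|---|---|---|---|---|---|
| 30 / 100 | 24 / 80 | 91.6% | 84.6% | 98.7% | 96.1% |
| 30 / 220 | 24 / 176 | 94.8% | 89.3% | 99.4% | 97.9% |
| 60 / 190 | 48 / 152 | 99.7% | 98.8% | >99.9% | 99.95% |
| 90 / 160 | 72 / 128 | >99.9% | 99.7% | >99.9% | >99.9% |

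The last three pairs each total 250, the full enrolment, so for them the 20% has plainly not been taken off. The pair 30/100 totals 130 without explanation, and its 84.6% applies only if 130 is an enrolled count.

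**4. Adding clustering.** The protocol gives no ICC and no number of other centres. Assumptions: ICC 0.05, six equal PTMS centres, 30 equal other centres. Variance per arm is v = SD² × [1 + (m − 1) × ICC]/n, with m patients per centre. At SD 10 with 20% missing:
- 24 vs 80: m = 4 and 2.67; v = 100 × 1.15/24 + 100 × 1.083/80 = 4.792 + 1.354; SE 2.479; δ = 2.824.
- 24 vs 176: m = 4 and 5.87; v = 100 × 1.15/24 + 100 × 1.243/176 = 4.792 + 0.706; SE 2.345; δ = 2.985.

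Power depends on the reference df. Satterthwaite uses (v₁ + v₂)²/(v₁²/5 + v₂²/29), which is 8.1 and 6.6. The alternative is the number of centres minus 2, which is 34.

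| Analysable | Satterthwaite | df = 34 |
|---|---|---|
| 24 / 80 | 69.9% | 78.3% |
| 24 / 176 | 71.7% | 82.6% |
| 48 / 152 | 89.7% | 94.8% |
| 72 / 128 | 94.8% | 97.3% |

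Assuming 5 patients per other centre instead of 30 centres, with df = centres minus 2, gives 76% and 83% for the two 30-patient scenarios. At ICC 0 the Satterthwaite method already gives 75.5% and 77.5%, so much of the drop under that method comes from having only six exposed centres rather than from the assumed correlation.

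**5. Dilution under the centre contrast.** If only half of the PTMS-centre patients take part (an assumption), a 7-point effect in participants becomes 0.5 × 7 = 3.5 points. Power at SD 10 with 20% missing is then 32%, 36%, 56% and 66% across the four pairs, before clustering.

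**The case against.** The best defence is that this is a secondary objective in a study described as explorative and descriptive. It did not set the sample size, and sections 9.7.7 and 9.9 already warn of selection bias and confounding. The wording of 9.7.5 may be shorthand for the centre contrast, since 9.5 itself uses participation and centre in one sentence. Centre effects and covariates are commonly left to the SAP. This limits the severity. It does not settle which contrast is meant, and the general warnings never mention referral for incompliance.

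Four stronger readings are tempting, and the documents do not support them.
- A reader might infer that >90% is a calculation error. It is not; it follows from its stated inputs.
- A reader might infer that participation biases adherence against the programme and depression or cognition in its favour. Incompliance is only one of three referral triggers, newly diagnosed patients are generally referred, and participants are volunteers, so the net direction is unknown.
- A reader might infer that no adjustment is planned anywhere. Section 9.7.4 has a multivariable model for the primary outcomes that includes PTMS participation, baseline depression, SDMT, quality of life, fatigue, self-management and new vs existing Betaferon use. What is missing is any named covariate for the 9.7.5 regressions; pre-study compliance is also absent from the 9.7.4 list.
- A reader might take 70-72% as the true power. That figure needs an assumed ICC, an assumed centre count and the more severe df choice.

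**Conclusion.** The point holds at moderate weight. The mismatch between the centre contrast (8.2, 9.5) and the participation regression (9.7.5) is in the text and needs no assumption. As worded, 9.7.5 is open to confounding by indication of unknown net direction.

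The power shortfall is real but local. With the plan's own 20% missing, only the 30-patient scenarios at SD 10 fall below 90%: 30 vs 220 by 0.7 points, and 30 vs 100 to 84.6% if those are enrolled numbers. The 60- and 90-patient scenarios, and everything at SD 8, stay above 90% on that correction alone. Under the clustering assumptions above, the 30-patient SD 10 scenarios come to about 70-83%, while the 60- and 90-patient scenarios stay at about 90% or more. None of these figures allows for dilution by non-participants at PTMS centres, which could matter more than either correction.

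**What to change.** In 9.7.5, make the 8.2 centre contrast the main PTMS analysis and show participants vs non-participants descriptively only. Bring the sentence in section 7 that confines PTMS endpoints to the six centres into line with this. Account for centre with a random effect or small-sample cluster-robust errors. Adjust for the baseline value of each outcome, all of which are already collected; for compliance, use last-month expected and true treatment days where available. Also adjust for Betaferon-naive vs ongoing. Name referral selection as a limitation in 9.7.7.

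In 9.5, restate power on analysable patients (24/80, 24/176, 48/152, 72/128) for both SD 8 and SD 10. State that it is not above 90% in the 30-patient SD 10 scenarios, give a labelled ICC range with the df method, and note that non-participants at PTMS centres dilute the 7-point effect.

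The change is to wording and analysis only; no new data are needed. The price is lower stated power, wider intervals and a diluted contrast.

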# 9.6 Data management

A Contract Research Organization (CRO) will be selected and assigned for EDC system development. The CRF will be part of the EDC system which allows documentation of all outcome variables and covariates by all participating sites in a standardized way. The injection-related data stored in the BETACONNECTTM will be downloaded via a USB cable to the computer of the attending physician from there it can be uploaded into the eCRF. A validated software application for this procedure has been specifically developed by the manufacturer of the BETACONNECTTM "Medicom" and is already in use in the non-interventional study BETAEVAL. Information on the EDC system is available upon request (see BF1502\_EDC\_manual\_final\_yyyymmdd, Table 2: List of stand-alone documents, Annex 1). Detailed information on data management Plan (DMP), which is available upon request (see BF1502\_DMP\_final\_yyyymmdd Table 2: List of stand-alone documents, Annex 1).

For information on quality control, refer to section 9.8.

## 9.7 Data analysis

#### 9.7.1 Statistical considerations

Statistical analyses will be of explorative and descriptive nature. P-values <0.05 will be considered as statistically significant unless stated otherwise.

All variables will be analyzed descriptively with appropriate statistical methods: categorical variables by frequency tables (absolute and relative frequencies) and continuous variables by sample statistics (i.e. mean, standard deviation, minimum, median, quartiles and maximum). Continuous variables will be described by absolute value and as change from baseline per analysis time point, if applicable.

All analyses will be performed for the total study population (overall analysis) or when defined otherwise within a valid subpopulation. Patients receiving at least one dose of Betaferon® will be included in the analysis. Whenever reasonable, data will be stratified by subgroups (e.g. age, gender, baseline characteristics).

There will be no further documentation of patients fulfilling the following criteria (end of observation visit will be documented): 1. patients terminating Betaferon® treatment including those stopping treatment overall or switching to other treatments; 2. patients lost to follow-up; and 3. patients choosing to terminate study participation for any reason. During the final visit (in case of premature termination) the investigator should try to identify the date, when Betaferon® treatment was discontinued. If this date cannot be identified or approximated, e.g. if a patient is lost to follow-up, the date of the last documented visit should be chosen. Further, the investigator should make every effort to identify the reason, why a patient decides to terminate the study. Reasons for study termination will be displayed using descriptive statistics.

All therapies documented will be coded using the World Health Organization – Drug Dictionary (WHO-DD). Medical history, any diseases and AEs will be coded using the latest Medical Dictionary for Regulatory Activities (MedDRA) version.

All statistical details including calculated variables and proposed format and content of tables will be detailed in the Statistical Analysis Plan (SAP). The SAP will be finalized before study database lock. The SAP is available upon request (see BF1502\_SAP\_final\_yyyymmdd Table 2: List of stand-alone documents, Annex 1).

The first pre-specified analyses will be performed after the dataset for the 12-month follow-up is complete, the final analysis will be performed at the end of the study, which is the date the analytical dataset is completely available (all data for the 24-month follow-up are available).

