Study size	The sample size calculation is based on Analysis of Variance (ANOVA) aiming to identify the number of patients needed to detect a given difference in compliance between three groups of patients, since the maximum number of groups or categories for our covariates under investigation will be three (e.g. smoking [current, past, never]). We have chosen a difference of 7% in adherence between groups as clinically meaningful. Overall comparison: to account for a standard deviation of 10% (alpha=0.1; power=0.80) and 20% incomplete or missing data, we will need to enroll a total of 240 patients. Pairwise comparison: to account for a standard deviation of 10% (alpha=0.05; power=0.80) and 20% missing or incomplete data we will need to enroll a total of 250 patients.
Data analysis	Statistical analyses will be of explorative and descriptive nature. All issues concerning patient validity, data consistency checks, permissible data modifications will be described in detail in the Data Management Plan. All statistical issues including calculated variables and proposed format and content of tables will be detailed in the Statistical Analysis Plan. All therapies documented will be coded using the World Health Organization – Drug Dictionary (WHO-DD). Medical history, any diseases and AEs will be coded using the latest Medical Dictionary for

	Regulatory Activities (MedDRA) version.
Milestones	Start of data collection: Q2 2015
	End of recruitment: Q4 2016
	End of data collection: Q4 2018
	Final report of study results: Q1 2019

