# 6 Milestones

Table 1 presents planned milestones for the project. These milestones are based on a timely review and approval of the project. Administrative changes to milestones due to delays in study preparation and enrollment do not require amendments to the protocol. Revised study timelines and milestones which do not constitute a need for a formal protocol amendment are kept as stand-alone document.

Definitions:

٠	Start of study:	first center initiated
•	Start of data collection:	FPFV
•	End of data collection:	LPLV
•	Recruitment period:	time from FPFV to LPFV
•	End of study:	12 months after database clean / database closure but no later than 24 months after last patient last visit
•	Observation period:	time-window for data collection (FPFV to LPLV)
•	Final report:	Final report of study results 12 months after database close

Table 1: Milestones

Milestone	Planned date
Start of study & data collection	Q2 2015
Recruitment period	Q2 2015 until Q4 2016
End of data collection	Q4 2018
Interim statistical analysis	primary analysis will be at 12 and 24 months after inclusion

Final report of study results	Q1 2019

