# 8 Research questions and objectives

#### 8.1 Primary objective

The primary objective of this study is to determine baseline predictors of adherence to Betaferon® treatment after 12 and 24 months (co-primary end-point).

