#### 9.7.4 Analysis of primary outcome(s)

Our primary analysis will be after 12 and 24 months of observation; however, we will also perform analyses for the visits in between.

For the analyses of our primary outcome compliance we will use descriptive statistics to characterize compliance (in percent) by calculating mean ( $\pm$ SD), median, min, and max. This will include a stratified analysis according to the patients' pre-study experience with the BETACONNECTTM, i.e. new patients vs. experienced patients.

We will then investigate the association between baseline covariates and compliance in percentage using Analysis of Variance (ANOVA) and linear regression. First, we will use ANOVA to investigate mean differences in compliance for each of the categorical covariates. Second, we will use linear regression with compliance as the dependent variable and each of the covariates as independent variables. We will investigate univariate associations and then build a multivariable-adjusted model accounting for all covariates. With respect to the ANOVA analysis we will chose covariates as potential predictors that show a univariate association in the overall comparison using the F-test with a  $p \le 0.1$  and further investigate those in pairwise comparisons using both univariate and multivariable models. Finally, employing linear regression models, we will use a stepwise selection procedure to determine predictors of compliance, considering all covariates as potential predictors.

For the analyses of our co-primary endpoints we will likewise use descriptive statistics to characterize persistence and overall adherence (yes, no) using category counts and frequencies (percentages). This will include stratified analyses according to the patients' pre-study experience with the IMPACT number 18016; BETAPREDICT; Version 1.0, 12 February 2015 Page 42 of 75

BETACONNECTTM, i.e. new patients vs. experienced patients. In further analyses we will use logistic regression to investigate the association between baseline covariates as the independent variables and persistence and overall adherence as the dependent variables. The regression analyses will include investigating univariate associations, multivariable-adjusted associations, and finally as stepwise selection procedure to determine predictors of persistence and overall adherence, similar to the analysis of the endpoint compliance.

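### The only SAP deadline, study database lock, falls after the 12-month primary analysis, so the details the protocol leaves open may be settled once those results are known

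*Protocol*

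**What the plan says.** Section 9.7.1 defers all statistical details, calculated variables included, to the SAP and sets its deadline: "The SAP will be finalized before study database lock". No earlier version, date or interim lock is given. Annex 1 lists the SAP as a draft with its date to be determined.

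The same section then describes two analyses. On the first: "The first pre-specified analyses will be performed after the dataset for the 12-month follow-up is complete". On the second: "the final analysis will be performed at the end of the study, which is the date the analytical dataset is completely available", meaning all 24-month data.

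The first of these is not a side analysis. Section 9.7.4 states: "Our primary analysis will be after 12 and 24 months of observation". The interim-analysis row of the milestone table in section 6 reads: "primary analysis will be at 12 and 24 months after inclusion". Section 8.1 puts both time points in the primary objective and calls them co-primary.

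**The concern.** A plan protects an analysis only if it is fixed before the results are seen. Here the deadline is tied to the end of the study, while half of the primary analysis is run on a dataset that is complete well before then. Read as written, the rule allows details of the primary analysis to be decided with the 12-month results in hand and then applied to the same patients at 24 months.

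This is not a complaint that SAP content is missing from the protocol. The deadline is something the protocol does state, and it is placed too late to support the claim, made in the same section, that the 12-month analyses are pre-specified.

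The setting makes open details matter. Section 9.7.4 lists 34 candidate predictors by my count, sections 9.1.1 and 9.3.1 define three adherence outcomes, and predictors are finally determined by stepwise selection. In that setting modest choices of coding or entry criteria can change which predictors are reported.

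**Working it through.** **Timing.** Inputs from the Abstract and section 6: "End of recruitment: Q4 2016"; end of data collection Q4 2018. From sections 9.2.7 and 9.3.8: about 24 months of follow-up per patient, with the 12-month visit as follow-up visit 2.

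- Check on the plan's own figure: Q4 2016 + 24 months = Q4 2018, which matches the stated end of data collection.
- 12-month dataset complete: Q4 2016 + 12 months = Q4 2017.
- Earliest study database lock, assuming that it follows the last patient's last visit: Q4 2018.
- Gap: Q4 2018 − Q4 2017 = 4 quarters, about 12 months.

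The gap is a planning inference. The protocol gives no calendar date for running the 12-month analysis. Cleaning before that analysis shortens the gap, cleaning before study lock lengthens it, and section 6 lets milestones move without an amendment.

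**What is already fixed.**

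- Section 9.3.1: the compliance formula, the definition of persistence, the rule for overall adherence (at least 80% compliant and not dropped out), and the ranking of the three outcomes.
- Section 9.7.4: ANOVA, linear and logistic regression, the F-test screen at p ≤ 0.1, the use of stepwise selection, the list of candidate predictors, and many cut-points (for example EDSS ≤3 against >3; relapses 0, 1, >1; number of concomitant diseases 0, 1, ≥2).
- Section 9.7.1: the fallback date for discontinuation when the true date is unknown.

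**What is left open.**

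- *Stepwise selection.* Section 9.7.4 names the procedure but no entry or stay criteria. The p ≤ 0.1 screen belongs to the ANOVA step; the stepwise step considers all covariates.
- *Covariate coding.* Concomitant diseases and concomitant medication appear as predictors in their own right, besides their counts, with no coding. Health-related quality of life is listed as one item, while section 9.3.2 describes eight SF-36 concepts. Employment has eight levels and education four in section 9.7.4, whereas section 9.5 assumes at most three categories for any covariate. No rule for collapsing them is given.
- *Analysis set.* Section 9.7.1 includes patients with at least one dose. Section 9.7.6 defines a full analysis set that needs baseline data and at least one post-baseline visit. Neither is named as the set for the primary outcome.
- *Drop-outs.* Overall adherence counts a drop-out as non-adherent. For compliance, section 9.5 expects 20% incomplete or missing data and says that accurate calculation will not be possible for these patients. Section 9.8.1 leaves missing data to the Data Management Plan, which is also undated in Annex 1.
- *Subgroups.* Section 9.7.4 makes the separate analyses by device experience depend on patient numbers and allows covariates to be removed if necessary, with no criterion.

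Each open item bears on the 12-month primary analysis, and none has to be settled before study lock.

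**The case against.** The strongest reply is that little is really at risk. The protocol, dated February 2015, already fixes the endpoints, models, screen and many cut-points. Section 9.7.1 calls the analyses explorative and descriptive, and section 9.9 warns that associations may be spurious, so no confirmatory claim would be invalidated. By calling the 12-month analyses pre-specified, the protocol shows the intent to have the specification ready beforehand, with study lock as an outer limit only. Study database lock is not defined, so it might be meant to include a 12-month data freeze.

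Much of this stands, and it narrows the point. A reader might infer that the primary rules as a whole could be written after the results; sections 9.3.1 and 9.7.4 rule that out. A reader might also infer that the 24-month analysis loses its value as an independent check. The protocol never offers it as one, and with the same patients and the same baseline covariates it could not be independent however early the SAP was signed. Nor does anything show that the sponsor plans to keep the SAP open; the text only permits it.

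The sequencing fault remains. The protocol defines no 12-month lock, and a statement of intent does not replace a deadline. Although explorative, the analyses use p < 0.05 as statistically significant (section 9.7.1), and section 8.2 wants the results to guide physicians.

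**Conclusion.** The point holds in limited form. The stated deadline does not secure pre-specification for one of two primary time points. The exposure is about four quarters on the planned milestones, assuming that the 12-month analysis follows soon after its dataset is complete and that study lock does not precede the last patient's last visit. It covers the five open items listed above, not the endpoint formulas or the modelling framework. What is at stake is the credibility of the claim to pre-specification in an exploratory predictor search; no error rate or confirmatory conclusion is shown to be wrong. It is worth correcting because the correction is cheap, but it does not undermine the study.

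**What to change.** In section 9.7.1 replace the deadline sentence with: *The SAP will be finalised and signed before the 12-month dataset is closed or extracted for analysis; later changes will be dated and labelled as made after the 12-month results.*

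The SAP should then settle the five open items. Because missing-data handling sits in the Data Management Plan, the SAP should state or cite the drop-out rule for compliance so that it falls under the same deadline.

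Cost: one sentence in the protocol, and the SAP work moves about one year earlier, from the run-up to Q4 2018 to the run-up to Q4 2017. Sample size, data collection and patient burden do not change.
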